7.3.2. Reporting Period

For SAEs, the active reporting period to the IRB and Pfizer begins from the time that the subject provides informed consent, which is obtained prior to the subject's participation in the study, i.e., prior to undergoing any study-related procedure and/or receiving TOFA, through and including 28 calendar days after the last administration of the investigational product.

SAEs occurring to a subject after the active reporting period has ended should be reported to the IRB, FDA, and PFIZER if the investigator becomes aware of them; at a minimum, all serious adverse events that the investigator believes have at least a reasonable possibility of being related to study drug are to be reported to the IRB, FDA and PFIZER.

AEs (serious and non-serious) will be recorded on the CRF from the time the subject has taken at least one dose of study treatment through last subject visit.

7.3.3 Definition of an Adverse Event

An AE is any untoward medical occurrence in a clinical investigation subject administered a product or medical device; the event need not necessarily have a causal relationship with the treatment or usage. Examples of AEs include but are not limited to:

- Abnormal test findings;
- Clinically significant symptoms and signs;
- Changes in physical examination findings;
- Hypersensitivity;
- Progression/worsening of underlying disease;
- Drug abuse;
- Drug dependency.

Additionally, they may include the signs or symptoms resulting from:

- Drug overdose;
- Drug withdrawal;
- Drug misuse;
- Drug interactions;
- Extravasation;
- Exposure in Utero (EIU);
- Exposure via breast feeding;
- Medication error;
- Occupational exposure.

7.3.4 Infections

All treated infections occurring during the study, including, but not limited to, respiratory infections, cutaneous infections, urinary tract infections and episodes of suspicious or febrile diarrhea, should be cultured and any identified organisms noted

in the case report form (CRF). Infections should be classified as either serious infections or treated infections, as defined below.

Serious Infections

A serious infection is any infection that requires hospitalization for treatment or requires parenteral antimicrobial therapy or meets other criteria that require it to be classified as a serious adverse event. A subject who experiences a serious infection must be discontinued from the study. This infection must be reported as a serious adverse event and should be listed as the reason for discontinuation in the electronic case report form (eCRF). Appropriate laboratory investigations, including but not limited to cultures should be performed to establish the etiology of any serious infection. All adverse events, including serious adverse events, must be reported as described in Section 7.7.1 on Adverse Event Reporting.

Treated Infections

A treated infection is any infection that requires antimicrobial therapy by any route of administration or any surgical intervention (e.g., incision and drainage). A subject who experiences a serious infection must be discontinued from the study. This information must be noted in the eCRF.

7.3.5 Abnormal Test Findings

The criteria for determining whether an abnormal objective test finding should be reported as an AE are as follows:

- Test result is associated with accompanying symptoms; and/or
- Test result requires additional diagnostic testing or medical/surgical intervention; and/or
- Test result leads to a change in study dosing or discontinuation from the study, significant additional concomitant drug treatment, or other therapy; and/or
- Test result is considered to be an AE by the investigator or PI.

Merely repeating an abnormal test, in the absence of any of the above conditions, will not constitute an AE. Any abnormal test result that is determined to be an error does not require reporting as an AE.

7.3.6 Serious Adverse Events

An SAE is any untoward medical occurrence at any dose that:

- Results in death;
- Is life-threatening (immediate risk of death);
- Requires inpatient hospitalization or prolongation of existing hospitalization;
- Results in persistent or significant disability/incapacity (substantial disruption of the ability to conduct normal life functions);

- Results in congenital anomaly/birth defect.

Medical and scientific judgment is exercised in determining whether an event is an important medical event. An important medical event may not be immediately life-threatening and/or result in death or hospitalization. However, if it is determined that the event may jeopardize the subject or may require intervention to prevent one of the other AE outcomes, the important medical event should be reported as serious.

Examples of such events are intensive treatment in an emergency room or at home for allergic bronchospasm; blood dyscrasias or convulsions that do not result in hospitalization; or development of drug dependency or drug abuse.

Protocol-Specified Serious Adverse Events

There are no protocol-specified SAEs in this study. All SAEs will be reported by the investigator as described in previous sections and will be handled as SAEs in the safety database.

Potential Cases of Drug-Induced Liver Injury

Abnormal values in aspartate transaminase (AST) and/or alanine transaminase (ALT) concurrent with abnormal elevations in total bilirubin that meet the criteria outlined below in the absence of other causes of liver injury are considered potential cases of drug-induced liver injury (potential Hy's Law cases) and will always be considered important medical events.

Subjects who subsequently present with AST or ALT ≥ 3 times the upper limit of normal (X ULN) concurrent with a total bilirubin ≥ 2 X ULN with no evidence of hemolysis and an alkaline phosphatase ≤ 2 X ULN or not available are asked to return to the investigational site and be evaluated as soon as possible, preferably within 48 hours from awareness of the abnormal results.

This evaluation may include laboratory tests, detailed history and physical assessment. In addition to repeating AST and ALT, laboratory tests should include albumin, kinase, total bilirubin, direct and indirect bilirubin, gamma-glutamyl transferase, creatinine prothrombin time (PT)/International Normalized Ratio (INR) and alkaline phosphatase.

A detailed history, including relevant information, such as review of ethanol, acetaminophen, recreational drug and supplement consumption, family history, occupational exposure, sexual history, travel history, history of contact with a jaundiced patient, surgery, blood transfusion, history of liver or allergic disease, and work exposure, will be collected.

Further testing for acute hepatitis A, B, or C infection and liver imaging (e.g., biliary tract) may be warranted. All cases confirmed on repeat testing as meeting the laboratory criteria defined above, with no other cause for liver function test abnormalities identified at the time should be considered potential Hy's Law cases irrespective of availability of all the results of the investigations performed to determine etiology of the abnormal liver function tests. Such potential Hy's Law cases should be reported as SAEs.

Study drug will be discontinued if liver injury is noted as defined above.

7.3.7 Hospitalization

AEs reported from studies associated with hospitalization or prolongation of hospitalization, are considered serious. Any initial admission (even if less than 24 hours) to a healthcare facility meets these criteria. Admission also includes transfer within the hospital to an acute/intensive care unit (e.g. from the psychiatric wing to a medical floor, medical floor to a coronary care unit, neurological floor to a tuberculosis unit). Hospitalization does not include the following:

- Rehabilitation facilities;
- Hospice facilities;
- Routine emergency room admissions;
- Same day surgeries (as outpatient/same day/ambulatory procedures).

Hospitalization or prolongation of hospitalization in the absence of a precipitating, clinical AE is not in itself an SAE. Examples include:

- Admission for treatment of a preexisting condition not associated with the development of a new AE or with a worsening of the preexisting condition (e.g., for work-up of persistent pre-treatment lab abnormality);
- Social admission (e.g., subject has no place to sleep);
- Administrative admission (e.g., for yearly physical exam);
- Optional admission not associated with a precipitating clinical AE (e.g., for elective cosmetic surgery);
- Hospitalization for observation without a medical AE;
- Pre-planned treatments or surgical procedures should be noted in the baseline documentation for the entire protocol and/or for the individual subject.

Diagnostic and therapeutic non-invasive and invasive procedures, such as surgery, will not be reported as AEs. However, the medical condition for which the procedure was performed should be reported if it meets the definition of an AE. For example, an acute appendicitis that begins during the AE reporting period should be reported as the AE, and the resulting appendectomy should be recorded as treatment of the AE.

7.3.8 Severity Assessment

If required on the AE CRFs, the investigator will use the adjectives MILD, MODERATE, or SEVERE to describe the maximum intensity of the AE. For purposes of consistency, these intensity grades are defined as follows:

- MILD- Does not interfere with subject's usual function.
- MODERATE -Interferes to some extent with subject's usual function.
- SEVERE- Interferes significantly with subject's usual function.

A severe event is not necessarily an SAE. For example, a headache may be severe (interferes significantly with subject's usual function) but would not be classified as serious unless it met one of the criteria for SAEs, listed above.

7.3.9 Causality Assessment

The investigator's assessment of causality will be provided for all AEs (serious and non-serious); the investigator must record the causal relationship in the CRF, as appropriate, and report such an assessment in accordance with the serious adverse reporting requirements if applicable. An investigator's causality assessment is the determination of whether there exists a reasonable possibility that the investigational product caused or contributed to an AE; generally the facts (evidence) or arguments to suggest a causal relationship will be provided.

If the investigator does not know whether or not the investigational product caused the event, then the event will be handled as "related to investigational product" for reporting purposes, as defined by the PI (see Section on Reporting Requirements).

If the investigator's causality assessment is "unknown but not related to investigational product", this will be clearly documented on study records. In addition, if the investigator determines an SAE is associated with study procedures, the investigator will record this causal relationship in the source documents and CRF, as appropriate, and report such an assessment in accordance with the SAE reporting requirements, if applicable.

7.3.10 Exposure In Utero

If a study subject or study subject's partner becomes or is found to be pregnant during the study subject's treatment with TOFA, the investigator will submit this information to the IRB, and the Pfizer Drug Safety Unit on a Serious Adverse Event Form and *Exposure in Utero* (EIU) Supplemental Form, regardless of whether an SAE has occurred. In addition, the investigator must submit information regarding environmental exposure to a Pfizer product in a pregnant woman (e.g., a subject reports that she is pregnant and has been exposed to a cytotoxic product by inhalation or spillage) using the EIU Form.

This will be done irrespective of whether an AE has occurred and within 24 hours of awareness of the exposure. The information submitted should include the anticipated date of delivery (see below for information related to termination of pregnancy).

Follow-up is conducted to obtain pregnancy outcome information for all EIU reports with an unknown outcome. The investigator will follow the pregnancy until completion or until pregnancy termination and notify Pfizer of the outcome as a follow up to the initial EIU Form. In the case of a live birth, the structural integrity of the neonate can be assessed at the time of birth. In the event of a termination, the reason(s) for termination should be specified and, if clinically possible, the structural integrity of the terminated fetus should be assessed by gross visual inspection (unless pre-procedure test findings are conclusive for a congenital anomaly and the findings are reported).

If the outcome of the pregnancy meets the criteria for an SAE (i.e., ectopic pregnancy, spontaneous abortion, intrauterine fetal demise, neonatal death, or congenital anomaly [in a live born, a terminated fetus, an intrauterine fetal demise or a neonatal death]), the investigator will follow the procedures for reporting SAEs.

Additional information about pregnancy outcomes that are reported as SAEs follows:

- “Spontaneous abortion” includes miscarriage and missed abortion.
- Neonatal deaths that occur within 1 month of birth should be reported, without regard to causality, as SAEs. In addition, infant deaths after 1 month should be reported as serious adverse events when the investigator assesses the infant death as related or possibly related to exposure to investigational product.

Further follow-up of birth outcomes will be handled on a case-by-case basis (e.g., follow-up on preterm infants to identify developmental delays). In the case of paternal exposure, the investigator will provide the study subject with the EIU Pregnancy Partner Release of Information Form to deliver to his partner. The Investigator will document on the EIU Form that the subject was given this letter to provide to his partner.

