5.1 Inclusion Criteria

1. Male or female ≥ 18 years of age and ≤ 45 years of age and > 40 kg body weight.
2. Fulfilled at least 4 out of the 11 Classification Criteria for SLE by the time of screening¹⁸.
3. Willing to give written informed consent, must fully understand the requirements of the trial, and must be willing to comply with all trial visits and assessments.
4. CLASI activity score of 8 or higher¹⁹ at screening and baseline despite standard of care therapy.
5. Stable dose of prednisone of ≤ 20 mg/day within 2 weeks of enrollment.

6. Female subjects of childbearing potential must use a highly effective method of contraception to prevent pregnancy (abstinence is considered highly effective) and must agree to continue to practice adequate contraception for the duration of their participation in the trial and for 28 days after their last dose of TOFA.
7. Female subjects of childbearing potential must have a negative serum pregnancy test at screening and a negative urine pregnancy test at Trial Day 1 before dosing.
8. For subjects receiving leflunomide treatment, total daily dose does not exceed 20 mg.
9. A negative QuantiFERON-TB Gold In-Tube test performed within the 3 months prior to screening, or within the screening period prior to baseline. A negative PPD test can be substituted for the QuantiFERON-TB.
10. Subjects either have protective varicella titers or evidence of having been vaccinated against varicella.

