Adverse Event Data Collection and Reporting Procedures. During a clinical trial, the reporting of adverse experience information can lead to important changes in the way a new treatment is developed, as well as provide integral safety data. All AEs will be reported on the AE pages of the CRF. All serious adverse events that occur, regardless of causality, will require immediate reporting (within 24 hours of knowledge to Pfizer. For any adverse event meeting the definition of fatal or “life threatening,” the investigator will notify Pfizer immediately. The IRB will be notified per IRB policy of SAE/AE that is both related to study drug and unexpected. All other AEs not fitting related/unexpected criteria will be reported to per IRB policy. Subjects or subjects’ partners who become pregnant during subject’s TOFA treatment will be reported on an SAE form with the addition of an *Exposure in Utero* (EIU) Supplemental Form, regardless of whether an SAE has occurred. Pregnancy SAE and EIU form will be submitted to Pfizer within 24 hours of awareness of the exposure and to the IRB per IRB policy.

See Protocol Section 7.7 Safety & Adverse Event Reporting for additional information.

WOMEN OF CHILDBEARING POTENTIAL

Patients must not be and should not become pregnant during exposure to study drug. Sexually active female participants must use an effective method of birth control during the study. The informed consent form will indicate that the investigator has reviewed information about pregnancy prevention for all women of childbearing potential. A serum or urine β -HCG will be performed at randomization. Pregnancy testing will be repeated throughout the study as deemed necessary by the treating physician.

L. RISKS & BENEFITS

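### Pregnancy reporting stops with the last dose, while contraception and SAE reporting run 28 days longer; the pregnancy text in Appendix 3 K also contradicts the inclusion criteria and the schedule

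*Combined protocol and SAP*

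**What the plan says.** **Reporting trigger.** Section 7.3.10 applies when a subject or a subject's partner "becomes or is found to be pregnant during the study subject's treatment with TOFA". It then calls for an SAE form and an EIU form whether or not an SAE has occurred, notice within 24 hours, and follow-up of the pregnancy to its end. Appendix 3, Section K repeats the duty for subjects or "partners who become pregnant during" the subject's TOFA treatment. Neither place goes past the last dose. Section 6.5 uses a wider phrase for female subjects, pregnancy during the study, but sends the reader back to 7.3.10 for follow-up.

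**Windows used elsewhere.** Inclusion criterion 6 in Section 5.1, repeated in Appendix 3 C, has women of childbearing potential "practice adequate contraception for the duration of their participation in the trial and for 28 days after their last dose of TOFA". Section 7.3.2 runs active SAE reporting "through and including 28 calendar days after the last administration of the investigational product". Section 7.1 adds one safety phone call 10 weeks after the last dose.

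**Testing and contraception.** Inclusion criterion 7 requires a serum test at screening and a urine test on Trial Day 1, and the Schedule of Assessments marks urine tests at repeated visits. Appendix 3 K says something different. On the entry test it has "A serum or urine β -HCG will be performed at randomization". Its contraception rule reads "Sexually active female participants must use an effective method of birth control during the study". For tests after entry, the appendix states "Pregnancy testing will be repeated throughout the study as deemed necessary by the treating physician".

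**The concern.** The plan asks women to avoid conceiving for 28 days after the last dose and actively collects SAEs over the same period, yet a conception in that period is outside the only clause that makes a pregnancy reportable as such. No reason is given for the difference. Safety is a primary objective, the population is aged 18 to 45, and Section 9 states that there will be no Data Safety Monitoring Board, so the written reporting rules decide what reaches the safety database.

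The second issue is that sites hold two sets of instructions. Section 9 refers to Appendix 3 as the detailed Data Safety Monitoring Plan, and its Section K differs from the main text on when to test, how often, and what contraception is required and for how long.

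**Working it through.** The plan states no figure for this point, so there is none to reproduce. The check is a comparison of passages plus simple arithmetic on the windows.

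**1. Windows side by side, in days after the last dose**

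| Rule | Where | Days covered after last dose |
|---|---|---|
| Contraception, female subjects | 5.1 criterion 6; Appendix 3 C | 28 |
| Active SAE reporting | 7.3.2 | 28 |
| EIU reporting, subjects and partners | 7.3.10; Appendix 3 K | 0 |

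The EIU trigger covers 0 of the 28 days that the other two rules cover.

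**2. Which pregnancies fall in the gap.** One that begins on treatment is covered whenever it is discovered, because becoming pregnant during treatment is enough to meet the trigger. The gap is therefore conception after the last dose.

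**3. Whether another rule catches it**
- Section 7.3.2 covers SAEs. An uncomplicated pregnancy meets none of the criteria in Section 7.3.6.
- Section 7.3.10 sends certain adverse outcomes to SAE procedures. Follow-up to learn the outcome, however, is attached to an EIU report, and here none is required. SAEs after the 28 days are reported only if the investigator becomes aware of them.
- Section 7.3.3 lists EIU only as a possible source of signs or symptoms that count as an AE. CRF recording of AEs ends at the last subject visit.
- The 10-week call is a general safety call, and no pregnancy question is stated.
- Section 6.5 is wider in wording but refers back to 7.3.10 and concerns female subjects only.

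**4. Relative size.** Uncovered share = 28 / (treatment days + 28).
- 76-week completer: 76 × 7 = 532 days; 28 / (532 + 28) = 28/560 = 5.0%.
- Subject stopped at week 8 (Section 6.5 discontinues subjects whose CLASI has not improved by then): 8 × 7 = 56 days; 28 / (56 + 28) = 28/84 = 33.3%.

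These are shares of calendar time, not probabilities that a pregnancy goes unreported.

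**5. Appendix 3 K against the rest of the plan**

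| Topic | Appendix 3 K | Elsewhere |
|---|---|---|
| Test at entry | One serum or urine test at randomization; the study is open-label with no randomization | Serum at screening and urine on Trial Day 1 (5.1 criterion 7; Appendix 3 C) |
| Later tests | At the treating physician's discretion | 12 marks in the urine-test row of the Schedule of Assessments, Trial Day 1 included (column alignment in the extracted table is uncertain) |
| Contraception | An effective method, during the study | A highly effective method, with contraception continued to 28 days after the last dose (5.1 criterion 6; Appendix 3 C) |

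**The case against.** The best defence is that 7.3.10 concerns exposure in utero, so tying it to treatment is a coherent scope. The documents call the 28 days a contraception and SAE-reporting period; they nowhere describe it as a period of fetal exposure. The only half-lives they give are 1.77 to 2.62 hours, from children with JIA. If adults are similar, a conception on day 10 comes about 240/2.62 = 92 half-lives after the last dose. That stands against any claim that such pregnancies are exposed. It does not explain why the plan asks for contraception and active SAE reporting over those days while leaving pregnancy out.

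There are also backstops: adverse pregnancy outcomes are handled as SAEs, late SAEs are reported if the investigator learns of them, and the 10-week call may bring a pregnancy to light. They narrow the gap to uncomplicated post-dose pregnancies, but create no duty to file an EIU form or follow such a pregnancy.

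On Appendix 3 K, the reference to randomization looks like leftover template text. Discretionary testing can be read as additional to the schedule, a subject who meets the stricter contraception standard meets both, and Appendix 3 C itself repeats the stricter criteria. These points make harm less likely. They do not remove the contradictory wording.

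Two stronger readings are tempting. A reader might infer that on-treatment testing is optional and that pregnancies will be missed on treatment. The schedule fixes repeated urine tests, so that would follow only if a site put Appendix 3 K above the schedule. A reader might also lengthen the gap by adding a detection lag for conceptions late in treatment. Those are already reportable under 7.3.10, and the documents give no figure for such a lag.

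**Conclusion.** The concern holds as an inconsistency in the reporting rules. An uncomplicated pregnancy conceived in the 28 days after the last dose, in a subject or a partner, has no required EIU form, 24-hour notice or outcome follow-up. That is 5% of the treatment-plus-28-day period for a 76-week completer and 33% for a subject stopped at week 8. Separately, the testing and contraception text in Appendix 3 K contradicts inclusion criteria 6 and 7 and the Schedule of Assessments.

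The conclusion rests on reading the treatment period as ending with the last dose. For partners, the comparison rests on the SAE window alone, because the contraception rule covers female subjects only. The documents do not support a statement that fetal exposure would be understated. With 20 planned subjects and no pregnancy endpoint, no PK or efficacy analysis is affected; the point concerns completeness of safety reporting and should be corrected.

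**What to change.** 1. In Section 7.3.10 and Appendix 3 K, extend the pregnancy-reporting trigger to 28 days after the last dose, matching Section 7.3.2, or state why it should differ. Align the wider phrase in Section 6.5 with the result.
2. Add a question on subject and partner pregnancy to the 10-week call already planned in Section 7.1.
3. Reconcile the testing and contraception text of Appendix 3 K with inclusion criteria 6 and 7 (Section 5.1 and Appendix 3 C) and the Schedule of Assessments, so that one rule stands. Which rule that should be is a clinical decision for the sponsor. Remove the reference to randomization.

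The cost is a few sentences of wording, one question on an existing call, and possibly a few more reports to file and follow.
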